6.6 Compliance Statement

This study will be conducted in accordance with this protocol, the International Council for Harmonisation Guideline for Good Clinical Practice E6 (ICH GCP, April 1996), Title 21 of the US Code of Federal Regulations (US CFR), the EU Directives 2001/20/EC and 2005/28/EC, and applicable national and local regulatory requirements.

7. STUDY PURPOSE AND OBJECTIVES

7.1 Study Purpose

The purpose of this study, in subjects with progressive measurable mCRC, is as follows:

- To evaluate the safety and tolerability of imalumab in combination with 5-FU/LV or panitumumab to determine the recommended phase 2 dose (RP2D) of each combination
- To compare the efficacy of imalumab in combination with 5-FU/LV versus SoC (investigator choice) as third or fourth treatment line in subjects with KRAS mut and/or NRAS mut tumors
- To compare the efficacy of imalumab in combination with panitumumab versus SoC (investigator choice) as third or fourth treatment line in subjects with KRAS wt and NRAS wt tumors

Furthermore, the pharmacokinetic (PK) profile of imalumab in combination with 5-FU/LV or panitumumab will be characterized, and limited pharmacodynamic (PD) serum markers will be explored.

7.2 Primary Objectives

The primary objectives of the study are:

- To determine the RP2D of imalumab in combination with 5-FU/LV or panitumumab (Part 1)
- To compare PFS between imalumab in combination with 5-FU/LV for subjects with KRAS mut and/or NRAS mut tumors or in combination with panitumumab for subjects with KRAS wt and NRAS wt tumors, versus SoC (investigator choice), as third or fourth treatment line (Part 2)

7.3 Secondary Objectives

7.3.1 Efficacy

The secondary efficacy objectives of the study are:

- To compare overall response rate (ORR) and clinical benefit rate (CBR) in subjects treated at RP2D with imalumab in combination with 5-FU/LV or panitumumab versus SoC (investigator choice) as third or fourth treatment line
- To compare OS of subjects who received imalumab in combination with 5-FU/LV or panitumumab versus SoC (investigator choice) as third or fourth treatment line

7.3.2 Safety

The secondary safety objective of the study is:

- To assess the safety and tolerability of imalumab in combination with 5-FU/LV or panitumumab

7.3.3 Pharmacokinetics

The secondary PK objective of the study is:

- To characterize the PK of imalumab in combination with 5-FU/LV or panitumumab

7.3.4 Quality of Life

The secondary QoL objective of the study is:

- To compare QoL of subjects who received imalumab in combination with 5-FU/LV or panitumumab versus SoC (investigator choice) as third or fourth treatment line

7.4 Exploratory Objectives

7.4.1 Pharmacodynamics

The exploratory PD objective of the study is:

- To characterize oxidized macrophage migration inhibitory factor (oxMIF) and total MIF in plasma prior to and during treatment with imalumab in combination with 5-FU/LV or panitumumab

7.4.2 Genetic Biomarkers

The exploratory genetic biomarker objective of the study is:

- To characterize tumor-associated genetic alterations in blood/urine (for all subjects treated with imalumab in combination with 5-FU/LV or panitumumab who provide consent for exploratory biomarker analyses)

The sponsor will obtain available historical tumor mutational testing results for subjects.

7.4.3 Quality of Life

The exploratory QoL objective of the study is:

- To compare disease-specific QoL and health utility in subjects treated with imalumab in combination with 5-FU/LV or panitumumab versus SoC (investigator choice) as third or fourth treatment line

8. STUDY DESIGN

8.1 Brief Summary

This open-label, randomized study to be conducted in approximately 40 study sites in the US and EU. The study comprises a Safety Run-in phase (Part 1) with 2 ascending doses of imalumab; and an exploratory phase (Phase 2a, ie, [Part 2]) with a 2-treatment-arm design. Approximately 78 to 90 subjects (approximately 12 to 24 subjects in Part 1 and 66 subjects in Part 2) with measurable mCRC, who have progressed after receiving at least 2, but no more than 3, prior treatment lines including SoC, will be enrolled in the study. Subjects can only participate in either Part 1 or Part 2 of the study. Adjuvant therapy in the metastatic setting (administered following a surgical procedure) and investigational products are included in the definition of a prior line of treatment for the purposes of this study.

In both parts, imalumab will be administered IV QW as part of a 4-week treatment cycle. Antitumor activity will be evaluated by the investigator after completion of every other treatment cycle (ie, every 2 cycles) using magnetic resonance imaging (MRI) or computerized tomography (CT) imaging and in accordance to Response Evaluation Criteria in Solid Tumors (RECIST) v1.1. Treatment will be continued until disease progression, unacceptable toxicity, withdrawal of consent, or for any other reason as detailed in Section 9.3.

8.2 Overall Study Design

8.2.1 Part I: Safety Run-In

Subjects will be enrolled into 2 sequential cohorts, with a minimum of 3 and a maximum of 6 subjects per cohort. Subjects will receive imalumab at 7.5 and 10 mg/kg QW in combination with infusional 5-FU/LV given Q2W in subjects with KRAS mut and/or NRAS mut tumors, or in combination with panitumumab given Q2W in subjects with KRAS wt and NRAS wt tumors. Treatment will be administered in 4-week cycles and will continue until disease progression, unacceptable toxicity, withdrawal of consent, or for any other reason as detailed in Section 9.3.

The DRC will meet for safety reviews after 3 subjects in a dosing cohort have completed the first treatment cycle (ie, after 28 days) to decide if additional subjects must be enrolled or if the next dose level can be opened. For each combination, based on all data of all evaluable subjects, the DRC will determine the RP2D, or decide if an intermediate dose level must be explored. The RP2D will be used as the dose for Part 2.

See Section 15.4.1 for additional details on the DRC.

[figure not shown]
8.2.1.1 Stopping Criteria for Dose Escalation

For each combination, enrollment will proceed according to the following rules based on the occurrence of DLTs:

- If zero out of 3 evaluable subjects experience a DLT during the first 28 days after the first administration of study drug at the first dose level, the second dose level will be opened for enrollment after review of the safety data by the DRC
- If 1 out of 3 evaluable subjects experiences a DLT during the first 28 days after administration of study drug at the first dose level, 3 additional subjects will be enrolled at the first dose level, for a total of 6 evaluable subjects. After review of the safety data of all 6 evaluable subjects, the DRC will decide if the second dose level or a lower dose level will be explored
- If 2 or more evaluable subjects experience a DLT during the first 28 days after the first administration of study drug at the first dose level, the second dose level will not be open to enrollment, and the DRC will decide if a lower dose level will be explored

See Section 8.2.3 for DLT definition. See [Figure 1](#) for a schematic of the dose escalation.

Figure 1
Protocol 391401 Dose Escalation Scheme

Abbreviation: DLT=dose-limiting toxicity.

^a A subject is considered evaluable if he/she can be evaluated for adverse events during the first 28 days after first study drug administration, or is withdrawn from the study due to a DLT.

8.2.2 Part 2: Exploratory Phase 2a

This is a 2-treatment-arm phase using a 2:1 ratio for subjects to receive imalumab + 5-FU/LV or imalumab + panitumumab (Arm A) or SoC per investigator choice (Arm B). Within each stratum, subjects will be randomized in a 2:1 ratio to receive imalumab + 5-FU/LV (KRAS mut and/or NRAS mut tumors) or imalumab + panitumumab (KRAS wt and NRAS wt tumors) (Arm A) or SoC per investigator choice (Arm B). Randomization will occur via an Interactive Response Technology (IRT) System until the targeted number of subjects in each treatment arm is achieved. For each combination in Arm A, subjects will receive imalumab at the RP2D determined in Part 1 for the corresponding combination. Subjects in Arm A with KRAS mut and/or NRAS mut tumors will receive 5-FU/LV in addition to imalumab at the RP2D dose determined in Part 1. Subjects in Arm A with KRAS wt and NRAS wt tumors will receive panitumumab in addition to imalumab at the RP2D dose determined in Part 1. Subjects in Arm B with KRAS/NRAS mut or wt tumors will receive investigator's choice (SoC, including best supportive care). If investigator's choice is to give panitumumab, subjects must have KRAS wt and NRAS wt tumors. All subjects will be treated until disease progression, unacceptable toxicity, or withdrawal of consent.

An independent Data Safety Monitoring Board (DSMB) will review accumulating unblinded safety data of subjects in Part 2 on a quarterly basis. See Section [15.4.2](#) for additional details.

The effect of imalumab in combination with 5-FU/LV or panitumumab on tumor-associated genetic biomarkers will be monitored. Blood and urine samples will be collected from those subjects treated with imalumab in combination with 5-FU/LV or panitumumab who provide consent for this optional exploratory analysis. It is possible that blood/urine biomarkers may correlate with clinical outcome (safety and efficacy) in response to imalumab treatment.

8.2.3 Definition of Dose-Limiting Toxicity

A DLT is defined as any drug-related treatment-emergent adverse event (TEAE) (graded according to the National Cancer Institute Common Terminology Criteria for Adverse Events [NCI CTCAE] v4.03) that occurs during the first 28 days after treatment start and that meets any of the following criteria:

- Any \geq Grade 3 non-hematologic toxicity excluding:
 - a. Mucositis/stomatitis of Grade 3 that resolves to Grade 1 or less with supportive measures within 7 days
 - b. Diarrhea of < 3 days duration following adequate and optimal therapy

- c. Nausea and vomiting of < 3 days duration with adequate and optimal therapy
- d. Fatigue of < 7 days duration following initiation of adequate supportive care
- e. Alopecia
- f. Any single laboratory value out of the normal range that has no clinical significance and that resolves to \leq Grade 2 with adequate measures within 7 days; transient Grade 3 elevations (lasting < 5 days) of hepatic transaminases in the absence of simultaneous increase in serum bilirubin
- Any Grade 4 hematologic toxicity excluding:
 - a. Grade 4 neutropenia lasting for \leq 5 days and not associated with fever
 - b. Isolated Grade 4 lymphocytopenia without clinical correlate
- Grade 3 febrile neutropenia
- Grade 3 thrombocytopenia associated with bleeding
- Any life-threatening complication or abnormality not covered in the NCI CTCAE v4.03

In subjects treated with panitumumab, if a dermatologic reaction develops that is Grade 3 (NCI CTCAE v.4.03) or higher (or is considered intolerable), the dose modifications recommended in the product label will be implemented.³⁴

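### Three DLT exclusions (diarrhea, nausea and vomiting, fatigue) have no grade limit, so a short drug-related Grade 4 event, where CTCAE v4.03 has that grade, is not counted as a DLT

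*Protocol*

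**What the plan says.** The non-hematologic DLT criterion in protocol 8.2.3 starts at Grade 3 with no upper bound, so Grade 4 is inside the set from which the exclusions are taken. The exclusions are then worded in two ways.

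- **With a grade limit:** (a) "Mucositis/stomatitis of Grade 3 that resolves to Grade 1 or less with supportive measures within 7 days"; and, in (f), "transient Grade 3 elevations (lasting < 5 days) of hepatic transaminases in the absence of simultaneous increase in serum bilirubin".
- **Without a grade limit:** for diarrhea, exclusion (b) reads "Diarrhea of < 3 days duration following adequate and optimal therapy", which tests time and treatment only. Exclusion (c) is built the same way: "Nausea and vomiting of < 3 days duration with adequate and optimal therapy". For fatigue, exclusion (d) allows a longer period but again names no grade: "Fatigue of < 7 days duration following initiation of adequate supportive care".

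The list of DLT criteria closes with "Any life-threatening complication or abnormality not covered in the NCI CTCAE v4.03". The protocol synopsis and SAP section 2 repeat the three unlimited exclusions in the same terms.

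The DLT count is used twice. Protocol 8.2.1.1 uses it to decide whether the second dose level opens, the first cohort expands to 6, or the second level stays closed. Protocol 13.4.3.1 and SAP 8.1 define the RP2D as the highest dose examined at which fewer than 33% of evaluable subjects have a DLT in cycle 1.

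**The concern.** A Grade 3 limit cannot simply be read into (b) to (d). Grade 3 is written into (a) and into the transaminase clause of (f). Under the hematologic criterion, where some Grade 4 events are meant to be excused, Grade 4 is named. Exclusions (b) to (d) do neither. Taken as written, they excuse a brief, treated event of any grade.

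The closing criterion on life-threatening events does not bring such an event back, because it is restricted to events that CTCAE v4.03 does not cover.

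At stake is the primary safety outcome of Part 1 and the dose carried into Part 2. With 3 to 6 evaluable subjects per dose level, one uncounted subject can change the result.

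**Working it through.** The plan states no figure that depends on this wording, so there is none to reproduce. The check has two parts.

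**1. Effect of one excused event in a subject with no other DLT.** Inputs are the escalation rule (protocol 8.2.1.1) and the <33% criterion (protocol 13.4.3.1, SAP 8.1).

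| All Grade 4 events counted | As written | Consequence |
|---|---|---|
| 1/3 = 33.3%: expand to 6; fails <33% | 0/3 = 0% | second level may open after committee review; passes <33% |
| 2/3 = 66.7%: second level closed | 1/3 = 33.3% | expand to 6 |
| 2/6 = 33.3%: fails <33% | 1/6 = 16.7% | passes <33% |
| 1/6 = 16.7%: passes <33% | 0/6 = 0% | no change in the <33% test |

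So the event matters at the boundary, but not always.

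**2. How often the result would change.** The documents give no rate for short Grade 4 events of these types, so both inputs are assumptions: p, the chance that a subject has a counted DLT (5% to 30%), and q, the chance of an excused Grade 4 event in a subject without a counted DLT (1% to 5%). With subjects independent, the chance that the result differs is:

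- First-3 escalation rule (0, 1, or 2 or more): (1−p)³[1−(1−q)³] + 3p(1−p)²[1−(1−q)²]
- <33% test, 3 subjects: (1−p)³[1−(1−q)³]
- <33% test, 6 subjects: (1−p)⁶[1−(1−q)⁶−6q(1−q)⁵] + 6p(1−p)⁵[1−(1−q)⁵]

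Worked values:

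- First-3 rule, p = 0.05, q = 0.05: 0.8574 × 0.1426 + 0.1354 × 0.0975 = 0.1223 + 0.0132 = 0.135.
- <33% test, 3 subjects, p = 0.05, q = 0.05: the first term alone, 0.122.
- <33% test, 6 subjects, p = 0.15, q = 0.05: 0.3771 × 0.0328 + 0.3993 × 0.2262 = 0.0124 + 0.0903 = 0.103.

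| Range over p = 0.05 to 0.30 | q = 1% | q = 5% |
|---|---|---|
| First-3 rule | 1.9% to 2.8% | 9.2% to 13.5% |
| <33% test, n = 3 | 1.0% to 2.5% | 4.9% to 12.2% |
| <33% test, n = 6 | 1.2% to 2.0% | 7.2% to 10.3% |

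The size depends almost entirely on q.

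**The case against.** **The premise is not proved from the documents.** SAP 16.2 gives CTCAE grades for laboratory values only, and the severity mapping in protocol 12.1.2.1 applies only to events that CTCAE does not describe. Nothing shows which of the three terms has a Grade 4. This stands, and it is why the point is conditional. A reader might infer that all three exclusions excuse Grade 4 events; the documents do not support that. For a term with no Grade 4, adding the limit changes nothing.

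**Part 1 decisions have been taken.** SAP 5.4 records 10 mg/kg, the higher of the two planned doses, as the Part 2 dose, and the SAP is dated 2016 OCT 06. The escalation rule applies to the first dose level, so no planned decision under it remains. This also stands. It limits the wording change to any further or intermediate cohort and leaves a retrospective check for the completed ones.

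**The larger probabilities need generous assumptions.** With p and q both 5%, brief, treated Grade 4 events of these few types would be about as common as all counted DLTs. The single-agent Phase 1 experience (protocol 6.1.5.1 and 6.4.2.1: 48 subjects, the observed DLT in one subject at 50 mg/kg every 2 weeks, most related events mild or moderate) does not suggest that, although it is not combination data. The figures are illustrations only.

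**There are real safeguards.** Even after 0/3, "the second dose level will be opened for enrollment after review of the safety data by the DRC", and "based on all data of all evaluable subjects, the DRC will determine the RP2D". The Data Review Committee also reviews all safety data monthly (protocol 6.5), and the Medical Monitor sits on it (15.4.1). A life-threatening event is an SAE (12.1.1.1), reportable within 24 hours (12.1.2.3). Excessive toxicity stops the study (8.6). SAP Table 3 tabulates treatment-related and serious events by grade for each cohort. A separate Grade 3 or higher consequence of the event could itself be a DLT. These make it unlikely that such an event would go unseen. None puts it into the DLT count, and Table 3 neither isolates the first 28 days nor marks excused events.

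**Conclusion.** The gap in the wording is real and appears in all three places, but its severity is minor. For any of the three terms that CTCAE v4.03 grades at 4, a brief, treated, drug-related Grade 4 event in the first 28 days is left out of the escalation count and the <33% percentage. One such event can decide the result at 1/3, 2/3 or 2/6. The probability is not known: about 1% to 3% if q is 1%, and at most about 10% to 14%, depending on the rule, if q is 5%. Both rates are assumed, as is independence between subjects.

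A reader might go further and infer that a Grade 4 event was missed in Part 1, or that 10 mg/kg was wrongly chosen. The documents support neither. They report no such event, and the committee sets the RP2D on all the data rather than on the count alone.

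**What to change.** Insert the words Grade 3 at the start of exclusions (b), (c) and (d) in protocol 8.2.3, the synopsis and SAP section 2, to apply to any further or intermediate dose cohort. Exclusion (f) and the closing criterion can stay as they are; the first clause of (f) has no upper grade either, but it requires that the value has no clinical significance.

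For the completed Part 1 cohorts, keep the original DLT count. Beside it, report any Grade 4 event excused under (b) to (d), using the AE listings already planned in protocol 13.4.4.2 (grade, relation, onset and stop dates). State for each combination whether 10 mg/kg still meets <33% with those events counted.

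The cost is one added term in three places and one check from planned outputs. The downside is that, in a further cohort, a rare extra DLT could add three subjects or, as a second DLT, keep a dose level closed.

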8.3 Duration of Study Period(s) and Subject Participation

The overall duration of the study is anticipated to be approximately 21 months from study initiation (ie, first subject enrolled) to study completion (ie, last subject last visit). The recruitment period is expected to be 15 months. Study completion is estimated to occur when 75% of OS events have been reported.

Subject participation includes a maximum of 4 weeks for screening, and 30 (\pm 7) days for post-treatment safety follow-up. Subjects will receive treatment until disease progression, unacceptable toxicity, or withdrawal of consent. For subjects who have stopped study drug or have documented disease progression, post-study telephone calls to assess OS will be made by site staff every 3 months.

8.4 Outcome Measures

8.4.1 Primary Outcome Measure

The primary safety outcome measure is the occurrence of DLTs (Part 1).

The primary efficacy outcome measure is PFS defined as time between treatment initiation and tumor progression (per RECIST v1.1 criteria) or death from any cause, with censoring of subjects who are lost to follow-up or withdraw consent (Part 2).

8.4.2 Secondary Outcome Measures

8.4.2.1 Immunogenicity Outcome Measures

- Occurrence of binding and/or neutralizing anti-imalumab antibodies
- Incidence and severity of infusion reactions after imalumab

8.4.2.2 Safety Outcome Measures

- Occurrence of SAEs and/or TEAEs, regardless of causality or relationship to study drug and coded according to NCI CTCAE v4.03
- Other safety measurements: physical or instrumental examinations, electrocardiograms (ECGs), vital signs, and clinically relevant changes in instrumental examinations or laboratory values

8.4.2.3 Efficacy Outcome Measures

- Response evaluation according to RECIST v1.1
- OS, defined as time from randomization to death of any cause

8.4.2.4 Pharmacokinetic Outcome Measures

Imalumab plasma PK will be characterized using a population PK modeling approach, in combination with data from other studies. Results of population PK modeling will be reported in a separate report.

8.4.2.5 Quality of Life Outcome Measures

The QoL outcome measure uses the EORTC QLQ-C30.

8.4.3 Exploratory Outcomes Measure

The exploratory PD outcome measures include plasma levels of oxMIF and total MIF.

Genetic biomarkers will also be investigated as an optional exploratory outcome. Exploratory genetic biomarker outcome measures include tumor-associated genetic alterations of cfDNA in blood/urine, for subjects treated with imalumab in combination with 5-FU/LV or panitumumab who provide consent for these analyses. The sponsor will obtain available historical tumor mutational testing results for subjects.

The exploratory QoL outcome measures use the EORTC QLQ for colorectal cancer 29 (EORTC QLQ-CR29) and the European Quality of Life – 5 Dimensions questionnaire (EQ-5D). The EORTC QLQ-CR29 will be used as a supplement to the EORTC QLQ-C30 to assess the disease-specific aspects of colorectal cancer. The EQ-5D is a health utility measure.

8.5 Randomization and Blinding

This is an open-label study. In Part 2, randomization will occur to minimize bias and fulfill a 2:1 ratio between Arm A and Arm B. Prior to randomization, subjects will be stratified according to their KRAS and NRAS mutation status. Randomization will occur via an IRT System until the targeted number of subjects in each treatment-arm is achieved.

8.6 Study Stopping Rules

This study will be stopped if 1 or more of the following criteria are met:

- Excessive toxicity or clinically meaningful SAE that may pose significant health risks
- Decision by the sponsor to interrupt or terminate the study at any time for reasons including, but not limited to, safety or ethical issues or insufficient non-compliance

When feasible, the sponsor will provide advance notification to the investigator of the impending action prior to its taking effect. The sponsor will promptly inform all other investigators and/or institutions conducting the study if the study is interrupted or terminated for safety reasons, and will also inform the regulatory authorities of the interruption or termination of the study and the reason(s) for the action. If required by applicable regulations, the investigator must inform the IEC/IRB promptly and provide the reason for the interruption or termination.

8.7 Investigational Product and Standard Drugs

8.7.1 Packaging, Labeling, and Storage

8.7.1.1 Imalumab

Dosage Form: Injection, solution

Packaging: Imalumab (50 mg/mL) will be supplied as a ready-for-use, sterile, non-pyrogenic liquid preparation in single-dose glass vials of 5 mL (with acceptable fill variance from 5.45 to 5.85 grams).

Labeling: The product will be labeled according to the valid regulatory requirements for clinical studies.

Storage: Imalumab must be stored under refrigerated conditions (2° to 8°C or 36° to 46°F) in the original package to protect from light. Do not freeze the product. Do not use if expiration date is exceeded or carton is damaged.

